 - Screening or Week 0/Day 1 prandomization vital signs (taken in the sitting position) with a heart rate (HR) < 50 bpm OR systolic blood pressure (BP) < 90 mm Hg OR diastolic BP < 55 mm Hg. Vital signs may be repeated up to 3 times during a visit to confirm abnormal readings
 - Screening or Week 0/Day 1 prandomization electrocardiogram (ECG) with PR interval > 200 ms or Fridericia's corrected QT interval (QTcF) ≥ 450 ms in men or ≥ 470 ms in women
 - Start, stop, change, or planned change in dosage of any anti-arrhythmic drugs (Class I to IV) ≤ 1 week before screening or within 1 week before or after randomization
9. Forced expiratory volume at 1 second (FEV₁) or forced vital capacity (FVC) $< 70\%$ of predicted values and FEV₁/FVC ratio < 0.70 at screening
10. Uncontrolled diabetes as determined by hemoglobin A1c (HbA1c) $> 9\%$ at screening, or subjects with diabetes with significant comorbid conditions such as retinopathy
11. History of macular edema or retinopathy
12. History of active tuberculosis (TB), history of untreated or inadequately treated latent TB infection, active or latent TB infection at screening (refer to [Appendix 2](#) for details on TB screening requirements and interpretation of test results). The following are EXCEPTIONS to this exclusion criteria:

- Subjects with latent TB, who have been ruled out for active TB, have completed an appropriate course of TB prophylaxis treatment per national/local medical guidelines or WHO guidelines, have a chest radiograph without changes suggestive of active TB infection, and have not had recent close contact with a person with active TB are eligible to enroll in the study. It is the responsibility of the Investigator to verify the adequacy of previous TB treatment and provide appropriate documentation of treatment compliance
 - Subjects diagnosed with latent TB at screening, ruled out for active TB and received at least 4 weeks of an appropriate TB prophylaxis regimen may be rescreened for enrollment. Subjects will complete their prophylactic regimen during the trial
13. A clinically significant active infection (eg, serious and/or atypical) \leq 28 days prior to randomization, required intravenous medication \leq 14 days prior to randomization, or that may worsen (in the opinion of the Investigator) if the subject is treated with a drug having immunosuppressant effects (ie, etrasimod). Fungal infection of nail beds is allowed

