5. REMOVAL OF SUBJECTS FROM STUDY TREATMENT OR ASSESSMENT

5.1. Discontinuation from Study Treatment

A subject's double-blind treatment may be discontinued for any of the following reasons:

- Worsening of disease (Note: If a subject discontinues double-blind treatment at any time starting with the Week 12 assessment, the subject may be eligible to enter the APD334-303 OLE [Section 5.1.1])
- Adverse event that in the judgement of the Investigator and/or Medical Monitor the subject should not continue study treatment
- Subject noncompliance with the protocol or study treatment that is considered significant by the Medical Monitor
- Investigator decision
- Withdrawal by subject or parent/guardian
- Lack of efficacy
- Lost to follow-up
- Study termination by Sponsor
- Other, non-adverse event

A subject's double-blind treatment must be discontinued for any of the following reasons:

- Decline in PFT values (FEV₁ and/or FVC) below 50% of the predicted values
- Confirmed diagnosis of clinically significant macular edema
- Confirmed diagnosis of active TB
- Subjects who have a cardiovascular treatment-related symptomatic event (eg, chest pain, dizziness, palpitations, lightheadedness, shortness of breath, or syncope) associated with reduction of the heart rate or associated with clinically relevant ECG changes at any time during the 4-hour monitoring period on Day 1 or Day 2 (as applicable) (Section 9.4.2.1)
- Subjects who have not met the discharge criteria on Day 1 after ≥ 4 hours of extended monitoring, or Day 2 by 4 hours post-dose (Table 4).
- Pregnancy (Section 9.10.9)
- Suspected drug induced liver injury as defined by the 2009 FDA Guidance for Industry (FDA 2009)
 - ALT or AST $> 8 \times$ ULN
 - ALT or AST $> 5 \times$ ULN for > 2 weeks
 - ALT or AST $> 3 \times$ ULN and (total bilirubin $> 2 \times$ ULN or international normalized ratio > 1.5)
 - ALT or AST $> 3 \times$ ULN with the appearance of fatigue, nausea, vomiting, right upper quadrant pain or tenderness, fever, rash, and/or eosinophilia ($> 5\%$)

Because transient fluctuations of ALT or AST are common, and progression to severe drug-induced liver injury or acute liver failure is uncommon, automatic discontinuation of study treatment upon finding a greater than $3 \times$ ULN elevation of ALT or AST may be unnecessary.

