9.10.4. Pulmonary Function Test

Pulmonary function tests will be performed according to the Schedules of Assessments (Table 7 and Table 8) and includes FEV₁ and FVC measurements. All subjects will have PFTs performed at Screening, Week 12, and Week 52, or at the ET visit. PFTs occurring at the ET visit that are

within 4 weeks of the last assessment (eg, Week 12) will only be required if clinically indicated. The 2-Week Follow-Up visit assessment is only required if clinically indicated.

Subjects with a history of mild pulmonary disease (eg, asthma, chronic obstructive pulmonary disease) will have additional PFTs performed at Week 32. Subjects reporting respiratory adverse events such as dyspnea during the treatment period may return at an unscheduled visit for assessment per Investigator discretion; additional PFTs may be performed as clinically indicated.

Subjects experiencing a decline in PFT values (FEV₁ and/or FVC) below 50% of the predicted values must be discontinued from study treatment and scheduled for a follow-up visit.

When available, DLCO measurements will also be performed. When DLCO is not available, sites should consult the Sponsor or Sponsor's delegate. These tests will be performed at a qualified pulmonary function laboratory or respiratory department. Please refer to the American Thoracic Society/European Respiratory Society guidelines for standardization of spirometry and single breath determination of carbon monoxide uptake in the lung ([MacIntyre 2005](#), [Miller 2005a](#), [Miller 2005b](#)).

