^g During the specified full physical examination, specific systems (eyes, liver, skin, and joints) will be examined for EIMs.

- ^h Pulmonary function tests will include FEV₁ and FVC measurements. Where locally available, DLCO measurements will also be performed (sites where DLCO is not available should consult the Sponsor or Sponsor's delegate). The Week 32 assessment is only required for subjects with a history of mild pulmonary disease (eg, asthma, chronic obstructive pulmonary disease). The 2-Week Follow-Up visit assessment is only required if clinically indicated. Details regarding additional PFTs are provided in Section 9.10.4.
- ⁱ Details regarding ophthalmoscopy and OCT assessments are provided in Section 9.10.5. The 2-Week Follow-Up visit assessment is only required if clinically indicated.
- ^j Urine pregnancy test for women of childbearing potential. A monthly home pregnancy test in non-visit months should be performed in countries where allowed per local regulation and any positive result immediately reported to the study site and a serum pregnancy test performed for confirmation. If not allowed per local regulations, this pregnancy test will be performed on site during an unscheduled visit.
- ^k Clinical laboratory tests will include serum chemistry, hematology (including coagulation), urinalysis, and hs-CRP and should be obtained prior to the daily dosing.
- ^l Stool sample is for fecal calprotectin (all indicated visits) and bacterial culture, ova, and parasite evaluation for *C. difficile* assay at any point in the study when a subject becomes symptomatic, including worsening or return of disease activity.
- ^m To be read by a blinded central reader. If the ET visit is within 4 weeks of the last sigmoidoscopy and biopsy, these procedures do not need to be repeated.
- ⁿ Pharmacokinetic blood samples are to be collected pre-dose (within the 60-minute period prior to dosing). A PK sample should be taken, if possible, at the time of any SAE or adverse event leading to study treatment discontinuation. In addition, for subjects not enrolling into the APD334-303 study, a blood sample for PK should be drawn at the 2-Week and 4-Week Follow-Up visits. For all PK blood draws, the time of the last dose should be documented.
- ^o Blood samples for biomarkers should be collected on the indicated day prior to the daily dose as applicable. Biomarker sample collection is not required at ET visit.

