18.1.5. TEAEs of Special Interest

Categories of Targeted Medical Events (TMEs) and a list of preferred terms associated with these TME categories were developed based on the mechanism of action of etrasimod, prior experience with other agents acting via a similar mechanism, and disease-specific clinical judgment. In addition, where standard testing has been implemented to screen for potential AESI (eg, electrocardiograms, spirometry, serum transaminases, etc.), the relevant data will be reviewed to identify potential cases of AESI that investigators may not have identified and to provide quantitative data for AESIs. The proposed candidate terms will be reviewed to identify which events reflect AESI.

TEAEs of special interest will be summarized by category, subcategory, and PT by descending frequency by treatment group. Categories and subcategories of TEAEs of special interest are the following:

- Cardiovascular Events
 - Bradycardia
 - AV conduction delay
 - Hypertension
- Macular Edema
- Pulmonary Disorders
 - Airflow obstruction (forced expiratory volume in 1 second [FEV₁], forced vital capacity [FVC])
 - Decrease gas exchange (diffusing capacity of the lungs for carbon monoxide [DLCO])
- Infections
 - Severe infections
 - Opportunistic infections (Narrow)
 - Herpes simplex and herpes zoster

- Liver Injury
 - Liver transaminases elevation
 - Bilirubin elevation
- Posterior Reversible Encephalopathy Syndrome (PRES)
- Malignancies

For each category, subcategory, and PT, model-based analysis will be performed to compare treatment effect between etrasimod and placebo. An extended Cox regression model will be used to handle recurring AEs (Cao 2011). The stratification variables, naïve to biologic or JAK inhibitor therapy status at study entry (Yes or No), Baseline corticosteroid use (Yes or No), and Baseline disease activity (MMS: 4 to 6 or 7 to 9), will be included in the model. A subject with K events contributes (K+1) observations to the input data set; here K might be 0. The k-th observation of the subject identifies the time interval from the start date of the (k-1)-th event, or time 0 (if k = 1), to the start date of the kth event, k = 1, ..., K. The (K+1)-th observation represents the time interval from the K-th event to the date of censorship, ie, the date of last dose or date of last study visit up to Week 52, whichever is later. Hazard ratios, 95% CIs, and p-values for treatment effect comparison will be presented.

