18.7. Other Safety Assessments

18.7.1. Pulmonary Function Tests

The following pulmonary function test (PFT) measurements (actual and % Predicted) will be reported for this study:

- FEV₁
- FVC
- Total Lung Capacity (TLC)
- FEV₁/FVC ratio
- Forced Expiratory Flow (FEF) 25-75

- DLCO (if available)

The following summaries will be provided for PFT data:

- Value and change from Baseline by visit
- Incidence of markedly abnormal values by visit (Section 18.7.1.1)

All PFT data will be listed. A listing in subjects who ever reported an abnormality in PFT will also be provided, including a flag for whether markedly abnormal criterion is also met.

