18.7.1.1. PFT Markedly Abnormal and Potentially Important Criteria

Markedly abnormal quantitative PFT measurements will be identified in accordance with the following predefined markedly abnormal criteria:

- % Predicted FEV₁ < 50%
- % Predicted FVC < 50%
- % Predicted FEV₁/FVC ratio < 50%

Potentially important PFT measurements will also be identified using the criteria below:

- Decrease from Baseline > 20% in FEV₁, ie, percent change from Baseline < -20%
- Decrease from Baseline > 20% in FVC, ie, percent change from Baseline < -20%
- Decrease from Baseline > 20% in DLCO, ie, percent change from Baseline < -20%

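### Exclusion 9 sets no numeric bar to a screening FEV1 or FVC already below 50% predicted when the FEV1/FVC ratio is preserved, although a decline below 50% is a mandatory stop

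*Protocol*

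**What the plan says.** **Entry.** Exclusion 9 (Protocol 4.2, same wording in the synopsis) applies to FEV1 or FVC under 70% "of predicted values and FEV₁/FVC ratio < 0.70 at screening". Section 9.3.8 has FEV1 and FVC measured at screening, with DLCO where a site can do it, but adds no threshold.

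**Stopping.** Section 5.1 lists among the mandatory reasons to end treatment: "Decline in PFT values (FEV₁ and/or FVC) below 50% of the predicted values". Section 9.10.4 repeats it: "Subjects experiencing a decline in PFT values (FEV₁ and/or FVC) below 50% of the predicted values must be discontinued from study treatment". Neither mentions the ratio.

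**Reporting.** SAP 18.7.1.1 names "Predicted FEV₁ < 50" and "Predicted FVC < 50" (both in per cent) as separate markedly abnormal criteria. SAP 18.7.1 plans a table of "Incidence of markedly abnormal values by visit (Section 18.7.1.1").

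**Obstructive focus.** SAP 18.1.5 has a special-interest subcategory of "Airflow obstruction (forced expiratory volume in 1 second [FEV₁], forced vital capacity [FVC"]). Table 8, footnote h, expects some subjects with mild lung disease: "The Week 32 assessment is only required for subjects with a history of mild pulmonary disease (eg, asthma, chronic obstructive pulmonary disease").

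**The concern.** The protocol monitors lung function because of the drug's mechanism and experience with related agents (section 1.3). One would expect a level that forces a subject off drug also to be a level at which the subject does not start.

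That holds for the other mandatory stops in 5.1 that can be checked at screening. Macular edema, active tuberculosis and pregnancy are all excluded at entry. ALT and AST must be at most 2.0 times the upper limit of normal at entry, while the stops begin above 3 times. The lung function level is the exception.

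A subject could therefore take the first dose with FEV1 or FVC already under 50% predicted, unless the investigator uses judgement to keep that subject out. What is at stake is the safety of a rare subject and consistent handling across sites.

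**Working it through.** This is a check of logic. The plan gives no figure to reproduce.

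**Inputs**
- Exclusion 9: (FEV1 < 70% or FVC < 70%) and ratio < 0.70 (Protocol 4.2 and synopsis).
- Stop level: FEV1 < 50% or FVC < 50% (Protocol 5.1 and 9.10.4).
- Predicted FEV1/FVC ratio: not in the documents. I assume 0.80, with a range of 0.75 to 0.85.

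**Reading of the sentence.** If the ratio condition were attached only to FVC, the FEV1 limb would have no threshold at all. The reading in which both parts must hold is the only workable one.

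**Formula.** Measured ratio = predicted ratio × (FEV1 % predicted ÷ FVC % predicted).

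| FEV1 / FVC (% predicted) | Measured ratio at predicted 0.75 / 0.80 / 0.85 | Excluded by criterion 9? | Below the 50% level? |
|---|---|---|---|
| 45 / 45 | 0.75 / 0.80 / 0.85 | No / No / No | Yes |
| 48 / 46 | 0.78 / 0.83 / 0.89 | No / No / No | Yes |
| 40 / 45 | 0.67 / 0.71 / 0.76 | Yes / No / No | Yes |
| 49 / 60 | 0.61 / 0.65 / 0.69 | Yes / Yes / Yes | Yes |
| 45 / 80 | 0.42 / 0.45 / 0.48 | Yes / Yes / Yes | Yes |

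The gap is confined to profiles in which FEV1 and FVC fall together. When the two percentages are equal, the measured ratio equals the predicted ratio. The 45/45 example therefore escapes exclusion for any predicted ratio of 0.70 or more.

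**Width of the gap.** Criterion 9 needs FEV1% ÷ FVC% < 0.70 ÷ predicted ratio. That limit is 0.70/0.80 = 0.875 (0.70/0.75 = 0.933; 0.70/0.85 = 0.824).
- At FVC 49%, the subject is not excluded if FEV1 is at least 49 × 0.875 = 42.9% (range 45.7% to 40.4%).
- At FEV1 49%, the subject is not excluded if FVC is at most 49 ÷ 0.875 = 56.0% (range 52.5% to 59.5%).

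**Timing.** The Week 12 test is at Day 85 ± 7, so Day 78 to 92. It is the first scheduled on-treatment lung function test.

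**Other entry limits.** No other inclusion or exclusion criterion gives a number for lung function.

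**The case against.** The best answer is that entry and stopping rules do different jobs. Criterion 9 screens for obstruction, which fits the SAP's special-interest category. The stop targets deterioration on drug. Different thresholds are then not a contradiction in themselves, and I do not claim one.

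There is also cover. Exclusion 7 ends in a catch-all for serious systemic illness that endangers the subject, and an investigator looking at 45% and 45%, with chest X-ray and examination in hand, could well use it. After entry, section 9.1 sends immediate safety concerns to the Medical Monitor, section 5.1 lets the investigator stop treatment, and section 9.10.4 allows unscheduled tests when respiratory symptoms arise. All of this stands. It is discretionary, though: exclusion 7 neither names lung disease nor gives a number.

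Three stronger readings are tempting, and the documents do not support them.
- *The conjunction is a slip for a disjunction.* Excluding on either limb alone would bar anyone with a ratio under 0.70, including subjects with mild obstructive disease for whom the protocol plans an extra Week 32 test.
- *Nothing prevents sites from handling the same unchanged value differently.* The Medical Monitor route in 9.1 is a study-level check, though not a numeric rule.
- *The stop should be reworded to catch any on-treatment value below 50%.* A subject who enters at 45% and falls further is naturally caught already. Only an unchanged or improved value is unclear, and it shows no harm from the drug. Forced withdrawal would turn later missing assessments into nonresponse under Protocol 10.4 and SAP 16.1.2.

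On reporting, an unchanged low value would count in the by-visit table of markedly abnormal results. The SAP also reports change from Baseline and flags falls of more than 20%, so a pre-existing low value can be told apart from a drug effect.

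**Conclusion.** The point holds as a narrow gap at entry. A subject with a preserved ratio and FEV1 or FVC already under 50% predicted meets no numeric exclusion, although the same protocol treats a decline below that level as a reason to end dosing. Whether such a subject is kept out rests on judgement.

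The severity is minor. The documents give no frequency, so the number affected is unknown and probably very small. The percentages under working show only how wide the gap is, and they rest on an assumed predicted ratio of 0.75 to 0.85. The gap itself does not depend on that range. No effect on the efficacy analysis is claimed.

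**What to change.** Keep the obstructive criterion unchanged. Add to exclusion 9, in section 4.2 and the synopsis: *or FEV1 or FVC < 50% of predicted values at screening, regardless of the FEV1/FVC ratio*.

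Leave the stopping rule in 5.1 and 9.10.4 alone. The entry limit closes the gap for new subjects, and anyone already enrolled below 50% can be referred to the Medical Monitor under 9.1.

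No extra test is needed, because FEV1 and FVC are already measured at screening. Subjects with mild asthma or chronic obstructive disease stay eligible on the current terms unless a value is below 50%. The cost is a protocol amendment, which needs ethics committee approval before use (section 11.2), and a few more screen failures.

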5. REMOVAL OF SUBJECTS FROM STUDY TREATMENT OR ASSESSMENT

5.1. Discontinuation from Study Treatment

A subject's double-blind treatment may be discontinued for any of the following reasons:

- Worsening of disease (Note: If a subject discontinues double-blind treatment at any time starting with the Week 12 assessment, the subject may be eligible to enter the APD334-303 OLE [Section 5.1.1])
- Adverse event that in the judgement of the Investigator and/or Medical Monitor the subject should not continue study treatment
- Subject noncompliance with the protocol or study treatment that is considered significant by the Medical Monitor
- Investigator decision
- Withdrawal by subject or parent/guardian
- Lack of efficacy
- Lost to follow-up
- Study termination by Sponsor
- Other, non-adverse event

A subject's double-blind treatment must be discontinued for any of the following reasons:

- Decline in PFT values (FEV₁ and/or FVC) below 50% of the predicted values
- Confirmed diagnosis of clinically significant macular edema
- Confirmed diagnosis of active TB
- Subjects who have a cardiovascular treatment-related symptomatic event (eg, chest pain, dizziness, palpitations, lightheadedness, shortness of breath, or syncope) associated with reduction of the heart rate or associated with clinically relevant ECG changes at any time during the 4-hour monitoring period on Day 1 or Day 2 (as applicable) (Section 9.4.2.1)
- Subjects who have not met the discharge criteria on Day 1 after ≥ 4 hours of extended monitoring, or Day 2 by 4 hours post-dose (Table 4).
- Pregnancy (Section 9.10.9)
- Suspected drug induced liver injury as defined by the 2009 FDA Guidance for Industry (FDA 2009)
 - ALT or AST $> 8 \times$ ULN
 - ALT or AST $> 5 \times$ ULN for > 2 weeks
 - ALT or AST $> 3 \times$ ULN and (total bilirubin $> 2 \times$ ULN or international normalized ratio > 1.5)
 - ALT or AST $> 3 \times$ ULN with the appearance of fatigue, nausea, vomiting, right upper quadrant pain or tenderness, fever, rash, and/or eosinophilia ($> 5\%$)

Because transient fluctuations of ALT or AST are common, and progression to severe drug-induced liver injury or acute liver failure is uncommon, automatic discontinuation of study treatment upon finding a greater than $3 \times$ ULN elevation of ALT or AST may be unnecessary.

Subjects who discontinue treatment prematurely, regardless of the reason, should be instructed to return for an Early Termination (ET) visit within 7 days of the last administration of study treatment (Table 7 and Table 8) and before initiation of any new treatments to complete all of the ET assessments. If a subject discontinues due to pregnancy, they are not required to complete the endoscopy. If the ET visit is within 4 weeks of the last sigmoidoscopy and biopsy, these procedures do not need to be repeated.

If the ET visit is ≥ 2 weeks of the last administration of study treatment, the 2-Week Follow-Up visit is not required; however, the 4-Week Follow-Up visit should be scheduled and completed. If the ET visit is ≥ 4 weeks of the last administration of study treatment, the 4-Week Follow-Up visit is not required unless the absolute lymphocyte count (ALC) is not within normal limits.

5.1.1. Discontinuation from Double-Blind Treatment for Disease Worsening

Starting with the Week 12 assessment, subjects whose UC condition in the opinion of the Investigator has not improved or has worsened, compared with baseline (Week 0/Day 1), may be eligible to enroll in the OLE Study (APD334-303) provided their ES is ≥ 2 and they meet one of the following entry criteria:

- RB subscore ≥ 2 at 2 timepoints at least 7 days and no more than 14 days apart
- RB + SF subscores ≥ 4 at 2 timepoints at least 7 days and no more than 14 days apart
- RB subscore ≥ 2 or RB + SF subscores ≥ 4 (in any order) at 2 timepoints at least 7 days and no more than 14 days apart

For subjects discontinuing prior to Week 52, an endoscopic evaluation is required to confirm eligibility for the OLE. An endoscopy should be performed upon the appearance of UC symptoms but no more than 14 days after the second timepoint for symptom criteria above; however, a proctosigmoidoscopy does not need to be repeated if performed within the last 4 weeks.

